#### Secondary Endpoints

- Patient time spent in hospital and in transit in total over pre-operative and perioperative journey (Part 1)
- Patient anxiety on day of surgery as measured using State trait anxiety questionnaire STAI-Y given on ward on morning of surgery (Part1).
- Number and length of patient hospital visits comparing preoperative visits (clinic visits, preoperative assessment, tracer injection visits, ward visits and operative visits) (Part 1).
- Safety of Magtrace® and efficacy adverse events relatable to tracers, number of nodes removed, number of nodes containing tracer, % of patients with detectable tracer in the axillary sentinel nodes (Part 1), can surgeons differentiate Magtrace® and Magseed signal®.
- Cost per episode and for total care (Part 1).
- Surgical start time, days of week of operating, and delays to getting patient to theatre. Delays will be recorded by asking the theatre team directly preoperatively whether they had to wait for the patient to arrive, and what the reason was, and also whether the list had to be rescheduled/ moved to accommodate a delay (Part 1).
- To map the current pathways of patient care (Part 1).
- Evaluation of the key aspects of care pathways important to patients and healthcare professionals in the management of breast cancer (Part 2).
- Preferences/overall satisfaction with care package for Magtrace vs.
   Technetium, from the perspective of patients and healthcare providers (Part 2).

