## Study design (Part 1)

For Part 1, time-driven and activity-based costing (TDABC) will be utilised. TDABC is a bottom-up approach to healthcare pathway mapping and costing, which records pathways observed during routine clinical practice, identifies all points and durations of interaction with healthcare providers therein; and assigns time-dependent costs to each constituent. This method of costing is far more granular than reference costingv and enables not only an estimation of the economic impact of care pathways, but also the implications for healthcare professionals and service planning. This is due to the ability to monitor the extent of patient-HCP interactions, and to determine the true 'time cost' of existing and novel care pathways. The costs of non-time-dependent activities, including tariff-based ancillary investigations, radiography, and outpatient services, are subsequently added, based on reference costs, to provide a representative activity-weighted cost per completed treatment episode.

This approach is common in health service research.vi The methodology is the most thorough and comprehensive way to determine the real-world impact of Magtrace® on both patient flow, and clinical involvement with patients vs. the current standard of care, highlighting differences in both resource use and care pathways therein. Highly accurate and internally valid, this approach would enable the comparison of both the efficiency of breast cancer excision, and the workload of healthcare providers, whether clinical, clerical, or simply observation. Combined, these factors will combine a holistic estimate of the expected difference between existing care, and a switch to widespread use of Magtrace®.

Prior to recruitment, research staff will begin by mapping the current pathways for breast cancer excision at Wythenshawe Hospital and providing a preliminary

assessment of the workload of all members of staff involved in the patient pathway, from the decision-to treat appointment through to completion of surgery. Using a Delphi-approach, and coordination with staff from the Nightingale centre they will determine an outline of the basic resources involved, including staff costs (time, grade), radiography, inpatient and add-on costs.

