- Follow-up phone call to patient more than 24 hours after invitation (by breast research nurse);
- Study visit 1 Consultation with patient consent taken for study. Eligibility confirmed and baseline data recorded. Randomisation occurs. Placement of Magseed® device, and anaesthetic assessment performed.
- Study visit 2a day before surgery patients in the control group will receive their technetium on the afternoon prior to surgery if they are in a Two day protocol.
- Study visit 2 day of surgery. Patient will receive Technetium injection if in
  the control group and on a One day protocol and will receive blue dye in
  theatre if deemed clinically necessary. Patients in the Magtrace group will
  receive their Magtrace® injection. All patients will receive breast surgery.
  Participants will be asked to complete a single anxiety questionnaire on day of
  surgery.

 Study visit 3 – Routine follow-up done remotely without patient – Adverse effects recorded, oncological outcomes recorded.

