## 5. Selection and Withdrawal of Subjects

#### 5.1 Informed Consent

Consent for Part 1 of the study will be taken by a Consultant Breast Surgeon or Research Nurse. This consultant or research nurse will be authorised to take consent by the Chief Investigator of the study and will have received training about the study and written information about the study. This consent process will take place at Study Visit 1, for Part 1 patients, more than 24 hours after initial invitation to take part in the study. Consent for Part 2 (Focus Group & Survey) will be undertaken by the same staff members but will be taken at the time of introduction of the study to the patient or healthcare professional.

## 5.2 Inclusion Criteria - Part 1

- Participant is willing and able to give informed consent for participation in the study;
- Female, aged 18 years or above;
- Diagnosed with invasive breast cancer
- Willing to allow his or her General Practitioner and consultant, if appropriate, to be notified of participation in the study;

- Undergoing breast conservation surgery requiring Magseed® localisation and sentinel node biopsy
- All MRIs must be completed prior to Magseed® insertion

#### 5.3 Exclusion Criteria – Part 1

- Patients with a Pacemaker or implanted device in the chest wall;
- Patients who are pregnant or lactating;
- Patients who have received Magtrace® (iron oxide) injection in the previous six months;
- Patients with previous ipsilateral axillary surgery
- Patients whose breast and axillary surgery are not due to be performed synchronously.
- Patients following neoadjuvant chemotherapy
- Patients requiring an interpreter
- Patients involved in current research or have recently been involved in any research prior to recruitment

Patients who require MRI follow-up of the ipsilateral breast in the year following surgery (as Magtrace® may interfere with MRI)

All individuals will be considered for inclusion in this study regardless of age, disability, gender reassignment, marriage and civil partnership, pregnancy and maternity, race, religion and belief, sex, and sexual orientation except where the study inclusion and exclusion criteria EXPLICITLY state otherwise

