# 5.4 Screening and Eligibility Assessment

Potential participants for Part I will be identified at the Breast Multidisciplinary Meeting which occurs every morning in the Nightingale Breast Unit, MFT. Potential study participants will be patients who are newly diagnosed with breast cancer and screening will occur in this pre-clinic MDT meeting to see if they meet the eligibility criteria for the study. These patients will have a clinical consultation with a Breast Care Nurse and Breast Surgeon later the same day and their cancer diagnosis and care will be discussed. At the end of this discussion they will be offered further discussion about this study which they could be eligible for. The study will be briefly introduced by the clinician and then if the patient is potentially interested, they will be given a Patient Information Leaflet about the study and made aware that the study is completely

Title: Costs and benefits of Magtrace® in breast surgery Protocol V1 Date 03/08/2022

IRAS 293053 Page 31 of 45

optional and in the next few days the Research Nurse will contact them to ask if they are potentially interested in taking part.

Patients interested in taking part in the study will return for a further follow-up visit to discuss the study further and to confirm eligibility and to consent to the study at this point.

The screening process will include collection of the following data;

- Demographics age, sex, BMI;
- Current medications including anticoagulant medication;
- Pre-operative histology of the breast cancer;
- Oncological information size and location of lesion on imaging, clinical findings, radiological score;
- Medical history including implantable devices such as pacemakers or defibrillators:

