## 5.6 Withdrawal of Subjects

Safety of the study participants will be monitored by the Chief Investigator. It is unlikely there will be Serious Adverse Events directly related to the study as all of the interventions are now established in large studies with good safety profiles. Magtrace® has a risk of causing staining to the skin of the breast in the months following injection and that it appears as a brown stain that fades over time. This is similar to the blue dye that is often used in conjunction with Technetium to help identify the sentinel nodes in existing practice. The blue dye stains the skin Blue/grey compared to the brown of Magtrace®. The blue dye has a 1 in 10,000 risk of anaphylaxis, a risk not seen in Magtrace® injection.

Each participant has the right to withdraw study at any time. In addition, the investigator may discontinue a participant from the study at any time if the investigator considers it necessary for any reason including:

- Ineligibility (either arising during the study or retrospective having been overlooked at screening);
- Significant protocol deviation;
- Significant non-compliance with treatment regimen or study requirements;
- An adverse event which requires discontinuation of the study medication or results in inability to continue to comply with study procedures;
- Disease progression which requires discontinuation of the study medication or

results in inability to continue to comply with study procedures;

- Consent withdrawn;
- Lost to follow up.

It is understood by all concerned that an excessive rate of withdrawals can render the study un-interpretable; therefore, unnecessary withdrawal of patients should be avoided. Should a patient decide to withdraw from the study, patients will asked for a reason for withdrawal if they wish to offer one.

Withdrawal from the study will result in exclusion of the data for that participant from analysis.

The reason for withdrawal will be recorded in the CRF.

If the participant is withdrawn due to an adverse event, the investigator will arrange for follow-up visits or telephone calls until the adverse event has resolved or stabilised.

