#### 6 Trial Procedures – Part I

Assessments	Visit 2a	

	Baselin e Visit 1	Technetiu m (two day protocol only)	Surgery Visit 2	Post surgery Visit 3
		3,		
Informed consent and randomisation	Х			
Medical history	Х			
Magseed® insertion	Х			
CRFompletion including data transfer and query resolution	Х	Х	Х	Х
Concomitant medication check	Х			Х
Review/reporting of patient AEs/SAEs			Χ	Х
Anaesthetic assessment	Х			
Localise lesion with Magseed® during surgery			Х	
Perform sentinel node biopsy			Χ	
Data collection in theatre			Х	
Technetium injection		Х	X (one day protocol)	
Magtrace® injection			Х	

[figure not shown]

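### Patients are randomised before two Visit 1 steps shared by both arms, so anyone withdrawn at those steps becomes an avoidable exclusion after allocation (minor)

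*Protocol*

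**What the plan says.** The Part 1 visit list in Protocol section 4.2 begins Visit 1 with consent and continues: "Eligibility confirmed and baseline data recorded. Randomisation occurs. Placement of Magseed® device, and anaesthetic assessment performed". The section 6 schedule has a row "Informed consent and randomisation" in the Visit 1 column, the same column as Magseed insertion and the anaesthetic assessment. It gives no order within the visit.

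Section 5.2 requires that the patient be "Undergoing breast conservation surgery requiring Magseed® localisation and sentinel node biopsy". Both arms therefore have a Magseed. Sections 4.2 and 6.1 give Magtrace on the day of surgery; section 4.2 gives Technetium that day or, on the two-day protocol, the afternoon before.

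Section 5.6 lists among the reasons for discontinuing a participant "Ineligibility (either arising during the study or retrospective having been overlooked at screening", and then states: "Withdrawal from the study will result in exclusion of the data for that participant from analysis". Section 4.2 plans for 20 patients with data in each arm.

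**The concern.** Randomisation is best placed as late as practicable before care in the two arms diverges. Events before that point can then remove patients without disturbing the randomised comparison. Here the allocation is made earlier than any scheduled procedure needs it, ahead of two steps at which a patient's route to the planned surgery could change.

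Such a patient, if withdrawn, is lost after the arm is known, and the section 5.6 rule deletes the data already collected. Part 1 describes no blinding, so the decision to withdraw someone can be taken by people who know the allocation. The staff placing the Magseed and doing the assessment may know it too. At stake are a few avoidable exclusions in a small comparison and some loss of the protection that randomisation gives.

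**Working it through.** **Order of events.** Setting the sections side by side:

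- Section 4.2, Visit 1: consent, eligibility and baseline data, randomisation, Magseed placement, anaesthetic assessment.
- Section 4.2, Visit 2a: Technetium on the two-day protocol. Visit 2: Technetium on the one-day protocol, or Magtrace.
- Section 6: the Visit 1 items share a column and the tracer injections fall at Visits 2a and 2. This agrees with section 4.2 on the visit but is silent on order within it.

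The first scheduled difference between arms is therefore at Visit 2a or 2. No scheduled Visit 1 procedure uses the allocation.

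**What happens to a patient withdrawn at these steps.** Section 5.6 allows discontinuation for ineligibility arising during the study, among other reasons, and excludes withdrawn participants' data. Together with the order above, such a patient is a post-randomisation exclusion. Had the envelope been opened after both steps, the same patient would never have been randomised.

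**Size.** The protocol gives no power calculation, dropout rate or failure rate for Part 1, so there is no figure to reproduce. The rates below are assumptions. Let f be the proportion withdrawn at either step, independently across 40 randomised patients.

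- Expected losses = 40f.
- Chance of at least one loss = 1 − (1 − f)^40.
- Number to randomise to keep 40 = 40 / (1 − f), rounded up.

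| f (assumed) | Expected losses of 40 | Chance of at least one | Randomise to keep 40 |
|---|---|---|---|
| 1% | 0.4 | 33% | 41 |
| 2% | 0.8 | 55% | 41 |
| 5% | 2.0 | 87% | 43 |
| 10% | 4.0 | 98.5% | 45 |

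One loss is 1/20 = 5% of an arm. The cost in precision is small: if four losses fell two per arm, the standard error of a difference would rise by a factor of √(20/18) = 1.054, about 5%. What matters more is that the exclusions come after allocation. Recruiting replacements would restore the numbers but not the randomised comparison.

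**The case against.** The strongest reply is that the loss is hypothetical. No rate is given, nothing says that a failed placement or assessment leads to withdrawal, and section 3 describes Magseed as standard of care at the site and validated in Manchester. Both arms undergo the same steps, so failures should be balanced unless knowledge of the arm influences them, and the documents contain no evidence that it does. The section 5.6 exclusion rule is the larger fault; the timing of randomisation only widens exposure to it. All of this stands, and it keeps the point minor.

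A second reply is logistic. Section 5.7 allows Visit 1 as little as one day before surgery. On the two-day protocol Technetium is given the afternoon before surgery, so Visits 1 and 2a could fall on the same day. Section 3.3 says Technetium is prepared off site and transported, and the Study Summary restricts the Magtrace arm to surgeons with five training cases. A later allocation could be tight in those cases. This also stands, as a constraint on the fix.

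Several stronger readings are tempting but not supported:

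- *A failed placement makes the patient ineligible.* The section 5.2 criterion is surgery that requires Magseed localisation, not successful placement.
- *The section 6 table puts randomisation ahead of medical history.* Its rows are not chronological: the tracer injection rows come after the sentinel node biopsy row. Section 5.4 also collects medical history at screening.
- *Visit 1 is wrongly counted as outcome.* The time endpoint is deliberately "Patient time spent in hospital and in transit in total over pre-operative and perioperative journey", and the visit endpoint names clinic visits and preoperative assessment. A component common to both arms cancels in expectation; it can cost precision but causes no bias. How much precision cannot be stated, because the documents give no variances.
- *The stopwatch must run from before consent.* The phrase "from the decision-to treat appointment through to completion of surgery" describes mapping done before recruitment. Section 4.2 has patients monitored after they consent.
- *Research minutes inflate the cost.* Section 5.4 says interested patients "will return for a further follow-up visit to discuss the study further and to confirm eligibility and to consent", but section 4.2 costs NHS resource use, and nothing says that consent or randomisation time is costed.

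**Conclusion.** The point holds in a limited form. Section 4.2 places randomisation before two shared steps that do not need it, and section 5.6 would turn a withdrawal at either step into a post-allocation exclusion. Under assumed rates of 1% to 10%, this affects 0.4 to 4 of 40 patients. That range assumes that every failure at these steps leads to withdrawal, which the protocol does not say. Any influence of known allocation on how the shared steps are done, or on who is withdrawn, is an inference. The severity is minor: a cheap improvement, not a defect that invalidates Part 1. It does not call for any change to the whole-journey time, visit or cost endpoints.

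**What to change.** 1. In section 4.2, make opening the envelope the last step of Visit 1, after Magseed placement and the anaesthetic assessment. In section 6, separate randomisation from consent in the schedule and note that it comes last at that visit.
2. In section 5.6, replace the blanket exclusion with a rule that all randomised patients who have not withdrawn consent for use of their data are retained and analysed as allocated. This also covers losses between Visit 1 and surgery, which reordering cannot prevent.

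The cost is reordering within one visit and a few sentences of amendment. Because section 4.2 expresses cost per completed treatment episode, the text should also say how a retained patient who does not complete the planned surgery is counted. The downside is that theatre and nuclear medicine learn the allocation slightly later on the day; the site should confirm that this is workable when Visit 1 is the day before surgery and the two-day Technetium protocol is in use.

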#### Study design & analysis (Part 2)

Discrete-choice experiment (DCE) methodology is well described in existing published literature; and used extensively to measure patients', and more recently healthcare providers', preferences for various aspects of healthcare services.viii In DCEs, respondents are given a hypothetical care scenario, typically comparing one package of care or pathway to another, and asked to choose which of the available options they prefer, by placing a tick in a box. In some cases, an 'opt-out' option is included, however this is unlikely, although not unheard of, in the case of non-palliative oncology. The options provided to respondents typically vary with respect to several characteristics which have previously been deemed to be important to the respondents undertaking the survey. This study will follow methodological guidelines from the International Society for Pharmacoeconomics and Outcomes Research (ISPOR)ix, identifying attributes of potential importance through discussions with experts in breast cancer excision and focus-groups.

For this research therefore, these attributes will be determined following focus-groups with representative patients and healthcare providers alike (n = 4-10 representatives per focus group and 2 focus groups). Examples of attributes of care which may be important to patients and healthcare providers, and may impact on satisfaction with care, include time spent in the department (1 hour, 2 hour, 4 hours, 8 hours), number of injections received during treatment episode (0,1,2,4), exposure to radioactive substances, or the number of separate visits to the hospital in the week prior to surgery (1,2,4). Once these attributes have been determined following focus-groups a DCE survey is developed, with several hypothetical care pathways presented, all differing slightly with regard to the attributes identified during the focus groups. This process is repeated with the values (levels) of the characteristics (attributes) changing randomly each time. The choices respondents make, i.e. which option they prefer and tick the box of, can be used to infer preferences for each level of each of the attributes included. For example if respondents, more often than not,

prefer the option with a lower number of visits to the hospital, all things being equal, we can identify that this is a factor affecting their satisfaction with care. An example DCE from an unrelated disease area is provided in Figure 2

Figure 2: Example DCE

	OPTION A	OPTION B
MANAGING THE CHILD	CONSULTANT	JUNIOR DOCTOR
PAIN OR DISCOMFORT EXPERIENCED BY CHILD FROM INVESTIGATIONS	MODERATE	LOW
LIKELIHOOD OF CHILD RECEIVING ANTIBIOTICS	수 다 다 다 다 다 다 다 다 다 다 다 다 다 다 다 다 다 다 다	
PERSONAL COST TO PARENT OF CHILD	£7	£20
TOTAL TIME SPENT IN EMERGENCY DEPT. BY CHILD	2 HOURS	BHOURS
USE A DIAGNOSTIC POINT-OF-CARE TEST AT TRIAGE?	>	8
I CHOOSE		

	OPTION A	OPTION B
MANAGING THE CHILD	NURSE PRACTITIONER	JUNIOR DOCTOR
PAIN OR DISCOMFORT EXPERIENCED BY CHILD FROM INVESTIGATIONS	MODERATE	Low
LIKELIHOOD OF CHILD RECEIVING ANTIBIOTICS		
PERSONAL COST TO PARENT OF CHILD	£7	£12
TOTAL TIME SPENT IN EMERGENCY DEPT. BY CHILD	4 HOURS	1 HOUR
USE A DIAGNOSTIC POINT-OF-CARE TEST AT TRIAGE?		8
I CHOOSE		

Generally, each respondent is given

between 12 and 20 discrete choice tasks, with the levels of the attributes to choose from changing each time. It is not uncommon in DCE application to include at least one, if not two tests of rationality. One is usually provided as the first task to test understanding of the problem (and ensure rationality of the responses received), and one as the final task to ensure that respondents have been paying attention all the way through the survey and not simply rushing through, or alternatively suffering from survey fatigue. These are usually choice tasks with one very obviously preferable situation (i.e. 1 hospital visit, no injections, and only 2 hours on site) vs. a clearly inferior alternative (4 hospital visits, 8 injections and 24 hours on site). If respondents fail either test of rationality by saying that they prefer the option which is inferior, their responses are excluded from formal analysis.

As a full factorial approach to the DCE, where respondents are asked to choose between each one of thousands of possible management scenarios is implausible, a D-optimal approach to designing the DCE will be taken with the use of the gold-standard DCE software, nGene. Once developed, all choice sets will be reviewed by the Principal Investigator (PI) for the study before being checked for understanding, interpretation, and grammatical errors by research staff. At this point, choice tasks may be supplemented with imagery and colour in order to improve retention and minimise cognitive burden. This has proved useful in other DCEs where the literary capabilities or perceived attention span of respondents may be limited, as may be the case in the event of illness x. It will also be necessary at this point to perform a pilot test among a small group of research staff, to ensure the survey can be completed in less than 15 minutes. Once all checks have been performed, choice-sets will be converted into an interactive PDF format, for use on laptops or tablet-PCs.

Once the cohort of respondents have filled in the survey using a tablet-PC, a mixedlogit regression (in the assumed case of expected heterogeneity in preferences), performed using Stata 14, is proposed to estimate preferences for the management of breast cancer excision, owing to the likelihood of significant intra-respondent heterogeneity, due to the wide-ranging epidemiology of breast cancer and the likelihood of widely differing ages and other baseline characteristics. As such, each individual preference observed is considered as a random draw from the underlying general population distribution. In addition to the main-effects model, sub-group models differentiated by characteristics such as patient age (patients), or healthcare provider role (in the case of healthcare providers) will also be estimated. As the experiment is yet to be finalised, with levels and attributes yet to be determined, the sample size required to detect statistically significant preferences, is currently difficult to pinpoint. In general, the rule of thumb for DCEs is that 100 responses (per group, HCPs and patients), is usually sufficientxi. However, using a conservative set of assumptions and applying Louviere's non-parametric assessment, we anticipate, based only on preliminary discussions with the PI, that a sample size of 22 to 55 patients and healthcare providers, as demonstrated in Figure 3 below:

Figure 3: Sample size calculation for DCE

$$N \ge \frac{1-p}{Tp(a^2)} \left[ \Phi^{-1} \left( \frac{1+\alpha}{2} \right) \right]^2$$

N = Sample size

P = Expected choice proportion (i.e. 50% if two choices to pick from, 33.3% if three choices, 25% if four choices). **IN OUR CASE 2** 

T = Number of choice tasks performed by each respondent **RANGE 12 to 20** 

 $\alpha$  = Confidence level (i.e. 95%, 99%) **RANGE 95 to 99** 

a = accuracy level (i.e. observed proportion within 10% of true one) 95%

 $\Phi^{-1}$  = Inverse normal distribution

=

22 (optimistic) > N > 55 (conservative)

This number of participants answering the DCE will provide information regarding which attributes, and therefore which features of existing and future care pathways, are most important to respondents, and which cause them the most dissatisfaction. The results are expressed as relative preferences, thereby indicating which of the attributes including are more important than the others, and by what magnitude. By providing the survey to both patients and healthcare providers involved in the delivery of care it will be possible to determine which things are most important to both groups, and determine the level of satisfaction (measured quantitatively), with existing care pathways (Technetium nuclear medicine) and using Magtrace. This may in turn make adoption and uptake of Magtrace easier or help assuage concerns from commissioners regarding non utilisation; if the evidence suggests that a change in care provision would constitute an improvement for patients and healthcare providers alike. Similarly, by sub-grouping patients and healthcare providers into smaller groups (by age (patients), or role (healthcare providers) for example), it can be possible to hone-in on what really matters most to each group, and where resistance to adoption of the technology is likely to be greatest. Combining the utility estimates for various aspects of care pathways, it will be possible to say that a move from the current standard of care to Magtrace, would result in an increase in utility/satisfaction with care of X% for patients and Y% for healthcare providers.

[figure not shown]

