## Part 2 - Survey recruitment

Both healthcare providers and patients will be invited to take part in the Discrete Choice Experiment, sample size is 200 with a minimum of 50 responses being by health care professionals. We will invite up to 150 patients who attend the Manchester University NHS Foundation Trust Breast Service to participate in the study. These will be patients who have undergone breast cancer surgery and so have some insight into the treatment pathway. The patients will be invited either before or after their clinic appointment to complete the survey. Participants will be recruited by research staff while present for a clinical appointment in the Nightingale centre. Upon consenting to hear about the study, patients and healthcare providers will be given a short synopsis of the study detailing the aims and providing a brief example of the survey questions, in the form of a patient information leaflet (paper or electronic). Following consent (either by paper forms or using a Tablet-PC), respondents will be asked to spend 10-15 minutes completing the survey. Informed consent will be implied via completion of the survey both online and paper. No patient identifiable information will be collected for the survey, only very basic baseline demographics including age (patients), role (in the case of healthcare providers) and how far they have travelled to the department that day (patients).

A minimum of 50 Healthcare providers will be invited to complete the survey electronically, this will be a mixture of breast surgeons, breast care nurses and breast radiologists. They will be invited via email, directly from the study team. This is a survey to establish their preferences towards the healthcare scenarios provided to them, as such their answers will be critical to understanding the perceived added value of Magtrace. These individuals will be given written information about the study as with the patients, in the form of a participant information sheet, and asked to complete a consent form to take part in the study (either by paper forms or using a Tablet-PC). Informed consent will be implied via completion of the survey both online and paper. No identifiable information will be collected about the respondent with the exception of some simple descriptors and demographics. A full step by step guide to this process is provided in Figure 4

[figure not shown]

Figure 4: Study flow for DCE

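### Figure 3 gives the DCE accuracy two values: the stated 22 to 55 should read 20 to 56 at 10% accuracy, and 50 healthcare professionals sit below its conservative end

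*Protocol*

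**What the plan says.** Section 10.1 of the protocol refers the sample size back to the design text, so the DCE calculation stands in Section 4.2, Study design & analysis (Part 2). That text says the attributes and levels are not yet fixed, which makes the required number hard to pin down. It cites a convention: "the rule of thumb for DCEs is that 100 responses (per group, HCPs and patients), is usually sufficient". It then turns from that convention to a formula ("applying Louviere's non-parametric assessment") and expects 22 to 55 patients and healthcare providers, without saying whether this is per group or for both groups together.

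Figure 3 prints the formula and annotates the inputs: two alternatives, 12 to 20 choice tasks, confidence 95 to 99. The accuracy line reads "a = accuracy level (i.e. observed proportion within 10% of true one) 95" (a percentage). The result line is "22 (optimistic) > N > 55 (conservative".

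The Study Summary and Section 5.5 present 150 patients and 50 healthcare professionals as participants. Part 2 - Survey recruitment asks for 200 in total with at least 50 HCP responses, but then plans to invite up to 150 patients and says "A minimum of 50 Healthcare providers will be invited to complete the survey electronically". Of respondents who fail a rationality test, the DCE text says that "their responses are excluded from formal analysis".

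**The concern.** Each annotated line in Figure 3 ends with the value used in this study. On the accuracy line that value is 95%, while the gloss beside it says 10%. N depends on the inverse square of the accuracy, so 5% against 10% changes it fourfold, and a reader cannot tell which accuracy is being claimed. The result line is also impossible as printed, since no number is both below 22 and above 55.

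The HCP group is where this matters most. The protocol calls HCP answers critical to understanding the added value of Magtrace, promises models by HCP role, and intends to report a percentage gain in satisfaction for HCPs separately from patients. If the accuracy claim is unclear, and the 50 may be invitations rather than usable surveys, the precision of that result is not fixed by the plan.

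**Working it through.** **Inputs.** The formula is the one in Figure 3: N ≥ (1 − p)/(T·p·a²) × z², with z the normal quantile at (1 + confidence)/2. For p, Figure 3 gives "Expected choice proportion (i.e. 50% if two choices to pick from" and marks two choices for this study, so p = 0.5 and the formula reduces to N ≥ z²/(T·a²). T runs from 12 to 20. At 95% confidence z = 1.960 and z² = 3.841; at 99%, z = 2.576 and z² = 6.635.

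**Reproducing the stated range.** Results at the four corners, rounded up in brackets:

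| Confidence, T | a = 0.10 | a = 0.05 |
|---|---|---|
| 95%, T = 20 | 3.841/0.20 = 19.2 (20) | 76.8 (77) |
| 95%, T = 12 | 3.841/0.12 = 32.0 (33) | 128.0 (129) |
| 99%, T = 20 | 6.635/0.20 = 33.2 (34) | 132.7 (133) |
| 99%, T = 12 | 6.635/0.12 = 55.3 (56) | 221.2 (222) |

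Taking the 95% literally as a = 0.95 gives less than one respondent at every corner. Only a = 0.10 comes near 22 to 55. The upper end matches apart from rounding (55.3 must go up to 56). The lower end is 20, not 22.

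**Where 22 could come from.** At 95% and T = 18, N = 3.841/0.18 = 21.3, which rounds up to 22. That would fit 20 tasks less two rationality tasks. The same deduction at the other end (T = 10, 99%) gives 6.635/0.10 = 66.3, so 67 rather than 55. The two printed ends do not share one treatment of T.

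**Accuracy of the planned groups.** Solving for a gives a = z/√(T·N).

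- 50 HCPs, 95%, T = 20: 1.960/√1000 = 6.2%
- 50 HCPs, 95%, T = 12: 1.960/√600 = 8.0%
- 50 HCPs, 99%, T = 12: 2.576/√600 = 10.5%
- 150 patients, 95%, T = 12: 1.960/√1800 = 4.6%
- 150 patients, 99%, T = 12: 2.576/√1800 = 6.1%

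At 99% and a = 0.10, T = 13 needs 6.635/0.13 = 51.04 (52) and T = 14 needs 6.635/0.14 = 47.4 (48). So 50 HCPs miss 10% only at 99% confidence with 12 or 13 tasks.

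**Role subgroups.** The recruitment text names three HCP roles. An equal split of 50 is about 17 each, giving 1.960/√(12 × 17) = 13.7%, or about 14%, at 95% and T = 12.

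**Counts.** Section 5.5 needs 150 patients, but the recruitment text invites at most 150, so every invited patient must respond and none may fail a rationality test. For HCPs the same section gives 50 once as a minimum of responses and once as a minimum of invitations. The documents give no exclusion rate. If 5 to 20% failed (an assumption), 50 completed HCP surveys would leave about 47 to 40, with accuracy 8.3% to 8.9% at 95% and T = 12.

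**The case against.** The strongest defence is that the 10% gloss is part of the protocol and reproduces the conservative figure. There is even a reading that joins the two accuracy values: 5 percentage points absolute is 10% of p = 0.5, and the absolute form p(1 − p)z²/(T·a²) with a = 0.05 gives the same 19.2 to 55.3. That makes 10% relative accuracy the likely intent. But it is not the formula printed, in which a is relative, so the input still needs one value. The labels optimistic and conservative also make the intended direction of the inequality clear, though the line remains wrong.

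A reader might infer four stronger things that the documents do not support.

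- That 22 to 55 cannot be derived at all. It nearly can at a = 0.10, and 22 itself arises inside the stated ranges at T = 18 and 95%.
- That 50 HCPs miss the protocol's own bounds. Fifty lies between 22 and 55. The 100 per group is a rule of thumb that the text moves past, not a bound it adopts.
- That the HCP group will lack the claimed accuracy. At 10% it has it at 95% confidence for every stated T, and at 99% from T = 14 upward.
- That only a fraction of 50 HCPs will be analysed, or that correlation between a respondent's choices multiplies N by a known factor. The 50 invitations are a floor, not a cap, and the same section asks for at least 50 responses. No response rate or correlation is given. The formula does treat choices as independent while the text expects preferences to vary, which calls for a caveat rather than a figure.

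**Conclusion.** Wrong as written; a moderate correction. The accuracy input has two values that lead to ranges four times apart (20 to 56 against 77 to 222), the lower limit of 22 is not the optimistic corner of the stated inputs, 55.3 should round up to 56, and the inequality is reversed. On the 10% reading the 50 HCPs are five below the stated conservative end and six below the recomputed one, with 6.2% to 8.0% accuracy at 95% confidence. The 150 patients clear both 56 and the rule of thumb. Separately, the recruitment text is inconsistent about whether 50 HCPs means responses or invitations, and its cap on patient invitations leaves no room for non-response or exclusion.

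This rests on a = 0.10 being the intent, on T counting informative tasks only, and on choices being independent. If the sponsor meant a = 0.05, 50 HCPs would fall below even the lowest figure (77), and the present target could not be defended by this formula. The DCE serves secondary endpoints; the primary endpoint, cost-effectiveness in Part 1, is untouched.

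**What to change.** In Figure 3, give a = 0.10 as the only accuracy value, state the range as 20 (optimistic) to 56 (conservative) per group, and turn the inequality round. Change the 22 to 55 in the text to match, and say whether T includes the rationality tasks.

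Add the accuracy that the planned groups deliver at 95% and T = 12: about 4.6% for 150 patients and about 8.0% for 50 HCPs. Note that these treat choices as independent and that 50 HCPs do not meet the 99%, T = 12 case.

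In Part 2 - Survey recruitment, define 150 and 50 as completed, analysable surveys after rationality exclusions, with invitations continuing until both are reached, and align the Study Summary and Section 5.5. Label the HCP role models as descriptive.

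The planned 200 need not increase. The cost is rewording, a slightly less favourable stated accuracy, and some extra invitations.
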